Study information

Title	Real-World (RW) Elranatamab Administration: Step Up Dosing (SUD), Treatment Patterns, and Healthcare Resource Utilization (HCRU) in Japan MDV Data (SUMMIT)
Protocol number	C1071048
Protocol version identifier	2.0
Date	15 September 2025
EU Post Authorization Study (PAS) register number	EUPAS1000000503
Active substance	L01FX32
Medicinal product	ELREXFIO™ (elranatamab)
Research question and objectives	
Research Question: What are the characteristics of adult patients with MM who initiate elranatamab in Japan, and the SUD process, treatment patterns, HCRU, and safety associated with elranatamab administration?
 
The following objectives will be assessed among patients with MM receiving elranatamab:
 
Primary objectives:
 
 • Objective 1: To describe patients with MM initiating elranatamab, including demographics, treatment and medical history. • Objective 2: To describe and characterize elranatamab utilization, including timing, administration and dosing, during the follow-up period, including the step-up dosing (SUD) period. 
Secondary objectives:
 
 • Objective 3: To describe HCRU and costs associated with elranatamab usage during the follow-up period, including the SUD period. • Objective 4: To describe the use of other treatments for MM including supportive therapy during the follow-up period. • Objective 5: To describe incidence and prevalence of cytokine release syndrome (CRS), immune effector cell associated neurotoxicity syndrome (ICANS), and cytopenias during the SUD period.

090177e1a4a71ff1\Approved\Approved On: 05-Nov-2025 14:15 (GMT)

	
• Objective 6: To describe infection incidence and prevalence during the follow-up period. 
Exploratory objectives:
 
• Exploratory Objective 1: To describe the use of supportive medications during the SUD period and administration of IVIG within the 30-day post-index period.
Country(ies) of study	Japan
Author	[REDACTED]

2. LIST OF ABBREVIATIONS

Abbreviation	Definition
ADL	Activity of Daily Living
AE	Adverse event
anti-CD38	Anti-CD38 Monoclonal Antibodies
BCMA	B-cell Maturation Antigen
BM	Bone Marrow
CAR-T	Chimeric Antigen Receptor T-cell
CCI	Charlson Comorbidity Index
CIOMS	Council for International Organizations of Medical Sciences
CM	Centimeter
CRS	Cytokine release syndrome
DPC	Diagnosis Procedure Combination
EC	Ethics Committee
ED	Emergency Department
EU	European Union
GDPR	General Data Protection Regulation
GPP	Guidelines of Good Pharmacoepidemiology Practices
HCPCS	Healthcare Common Procedure Coding System
HCRU	Healthcare Resource Utilization
ICANS	Immune effector Cell Associated Neurotoxicity Syndrome
ICD-10	International Classification of Diseases, 10 th revision
IMiD	Immunomodulatory Imide Drug
IP	Inpatient
IQR	Interquartile range
IRB	Institutional Review Board
ISPE	International Society for Pharmacoepidemiology
ISPOR	International Society for Pharmacoeconomics and Outcomes Research
ISS	International Staging System

090177e1a4a71ff1\Approved\Approved On: 05-Nov-2025 14:15 (GMT)

IVIG	Intravenous immunoglobulin
LB	Pound
MDV	Medical Data Vision
MM	Multiple Myeloma
NI	Non-Interventional
OP	Outpatient
OS	Overall Survival
PASS	Post-Authorization Safety Study
PI	Protease Inhibitor
PMDA	Pharmaceuticals and Medical Devices Agency
PPPD	Per Patient Per Day
PPPM	Per Patient Per Month
QW	Once weekly
Q2W	Once every two weeks
RAI	Relative Administration Intensity
RRMM	Relapsed/Refractory Multiple Myeloma
RW	Real-World
RWD	Real-World Data
SAP	Statistical Analysis Plan
SCT	Stem cell transplantation
SD	Standard Deviation
SUD	Step-Up Dosing
TCE	Triple-class exposed

090177e1a4a71ff1\Approved\Approved On: 05-Nov-2025 14:15 (GMT)

4. ABSTRACT

- **Title:** Real-World (RW) Elranatamab Administration: Step Up Dosing (SUD), Treatment Patterns, and Healthcare Resource Utilization (HCRU) in Japan MDV Data (SUMMIT)

Version: 2.0

Date: 15 September 2025

- **Rationale and background:** Despite treatment advancements, many MM patients experience relapse or refractory disease (RRMM), leading to poor prognosis and limited options. Elranatamab is the first bispecific B-cell maturation antigen (BCMA)-directed monoclonal antibody to receive approval from the Japanese Pharmaceuticals and Medical Devices Agency (PMDA) in March 2024. Elranatamab was approved for the treatment of patients with RRMM who have been exposed to at least three standard therapies including IMiD, PI, and anti-CD38, i.e. triple-class exposed (TCE). This study will leverage a Japanese hospital-based administrative health dataset to describe the RW administration of elranatamab, including patient selection, treatment patterns and healthcare utilization (HCRU) in an MM population.

- **Research question and objectives:**

Research question: What are the characteristics of adult patients with MM who initiate elranatamab in Japan, and the SUD process, treatment patterns, HCRU, and safety associated with elranatamab administration?

The following objectives will be assessed among patients with MM receiving elranatamab:

Primary objectives:

Objective 1: To describe patients with MM initiating elranatamab, including demographics, treatment and medical history.

Objective 2: To describe and characterize elranatamab utilization, including timing, administration and dosing, during the follow-up period, including the step-up dosing (SUD) period.

Secondary objectives:

Objective 3: To describe HCRU and costs associated with elranatamab usage during the follow-up period, including the SUD period.

Objective 4: To describe the use of other treatments for MM including supportive therapy during the follow-up period.

Objective 5: To describe incidence and prevalence of cytokine release syndrome (CRS), immune effector cell associated neurotoxicity syndrome (ICANS), and cytopenias during the SUD period.

Objective 6: To describe infection incidence and prevalence during the follow-up period.

Exploratory objectives:

Exploratory Objective 1: To describe the use of supportive medications during the SUD period and administration of IVIG within the 30-day post-index period.

- **Study design:** This is a retrospective observational study utilizing de-identified data from Japan Hospital administrative claims data (Medical Data Vision [MDV]).
- **Population:** The study population will include all adults aged 18 years or older with an MM diagnosis who initiate elranatamab on or after March 26, 2024 (PMDA Elrexfio approval date). Patients with evidence of clinical trial participation will be excluded.
- **Variables:** The following variables will be summarized and reported:

Exposure of interest:

Exposure is defined as at least one record of a hospital claim for elranatamab on or after March 26, 2024. All patients included in the study will be considered exposed. Analyses of outcomes during the SUD period will also be stratified based on types of elranatamab exposure during that time (i.e., complete and timely SUD, complete but not timely SUD, alternative SUD). Clinical data will be collected from MDV hospital data.

Study outcomes:

Study endpoints include: elranatamab timing and dosing (i.e., types of doses, time between doses, relative administration intensity), HCRU and costs (i.e., IP/OP/ED claims and associated costs, degree of nursing), other MM treatment post elranatamab administration (i.e., PIs, SCT, supportive therapy), known adverse events (i.e., CRS events occurrence, frequency and associated length of stay, time from index to CRS event), infection (i.e., infection occurrence, time from index to infection, antibiotics), and supportive medication (i.e., IVIG, acetaminophen, dexamethasone).

Covariates:

Covariates will include baseline demographics (i.e., age, sex, weight etc.), and baseline clinical characteristics (i.e., comorbidities and treatment history).

- **Data sources:** The MDV database is a comprehensive resource containing administrative data from over 540 hospitals in Japan. This dataset includes information on demographics, mortality, labs, IP, OP, ED claims, treatments, procedures and costs of approximately 50 million patients. MDV is an aggregated, de-identified dataset where no patient can be individually identified and therefore no patient consent is required.
- **Study size:** This is a retrospective descriptive study with no a priori hypotheses; therefore, sample size calculations are not applicable. As of February 2025, MDV included 128 patients that had at least one hospital claim for an elranatamab administration.
- **Data Analysis:** Descriptive statistics will be used for all objectives, and no hypothesis testing will be conducted. Incidence and prevalence calculations will be conducted.

- **Milestones:** The study will be registered in the HMA-EMA Catalogues of RWD studies on July 14, 2025, followed with data collection commencing on July 15, 2025. An interim study analysis is scheduled for release on September 30, 2025. Data collection will conclude on June 30, 2026, followed by the final study report on November 30, 2026.

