SUD period: defined as the period between a patient's first 44mg/1.1mL vial of elranatamab and first 76mg/1.9mL vial of elranatamab, inclusive. See Section 9.3.1 and Annex 1 for more details. Within the SUD period, three sub-periods are identified:

- **Overall:** defined as the period between first 44mg/1.1mL vial and first 76mg/1.9mL vial of elranatamab.
- **First 44mg/1.1mL vial – Second 44mg/1.1mL vial:** defined as the period between the two 44mg/1.1mL vials of elranatamab, if second 44mg/1.1mL vial is administered.
- **Second 44mg/1.1mL vial – first 76mg/1.9mL vial:** defined as the period between the second 44mg/1.1mL vial and the first 76mg/1.9mL vial of elranatamab, if second 44mg/1.1mL vial is administered.

Follow-up period: defined as the period between the first hospital claim for elranatamab (index date) and the end of the hospital claim of the last elranatamab administration. Within this follow-up period, five sub-periods are identified (when sufficient follow-up time is available at the patient level). These sub-periods allow for reporting study endpoints across different phases of the follow-up period, and are based on expected dosing administrations and schedule of patients with switch to bi-weekly administrations from label guidance (see [Table 10. Dosing Schedule of Elranatamab during Follow-up Period for Patients Switching to](#)

[Q2W](#) and [Table 11. Dosing Schedule of Elranatamab during Follow-up Period for Patients staying on QW](#)):

- **Index date to day 8:** defined as the first 8 days post-index date, inclusive. Also defined as day 1 to day 8.
- **Day 9 to day 168:** defined as the period from day 9 to day 168 post-index date.
- **Day 169+:** defined as the period from day 169 post-index date to end of follow-up period.

- **Overall follow-up:** defined as the period from index date to end of follow-up period.

IVIG follow-up assessment period: defined as the 30-day window post index date. If a patient has fewer than 30 days of data available post to the index date, the assessment window will be equal to the maximum number of days available post to the index date.

CRS/ICANS follow-up assessment period: defined as the 14-day window post index date. If a patient has fewer than 14 days of data available post to the index date, the assessment window will be equal to the maximum number of days available post to the index date.

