9.3.1 Exposure Groups and Assessment Periods

[Table 1](#) outlines the variables to define exposure groups that will be used to identify patients and stratify analyses.

Table 1. Variables for Exposure

Variable	Role	Data Source	Operational Definition	
			Definition	Assessment Period(s)
Study population	Exposure	MDV	All patients with MM who have a hospital claim for elranatamab after March 26, 2024, and who meet the inclusion and exclusion criteria outlined in Sections 9.2.1 and 9.2.2.	Index date
SUD Exposure Group	Exposure	MDV	
Group A: Complete and timely SUD period
 
Patients in the study population with two 44mg/1.1mL vials (second 44mg/1.1mL vial is received 1 to 7 days after the first) and one subsequent 76mg/1.9mL vial between 1 to 7 days after second 44mg/1.1mL vial
 
Group B: Complete but not timely SUD period
 
Patients in the study population with two 44mg/1.1mL vials and one subsequent 76mg/1.9mL vial after the second 44mg/1.1mL vial, with one or both intervals between doses ranging from 8 to 14 days.
 
Group C: Alternative SUD period
 
 • Only one 44mg/1.1mL vial: patients in the study population with only one 44mg/1.1mL vial prior to receiving a 76mg/1.9mL vial • More than two 44mg/1.1mL vials: patients in the study population with more than 	SUD period

090177e1a4a71ff1\Approved\Approved On: 05-Nov-2025 14:15 (GMT)

Variable	Role	Data Source	Operational Definition	
			Definition	Assessment Period(s)
			
two 44mg/1.1mL vials prior to receiving a 76mg/1.9mL vial
 
 Extremely untimely: patients in the study population with more than 14 days between the first and second 44mg/1.1mL vial or between the second 44mg/1.1mL vial and the first 76mg/1.9mL vial 
Note that patients who received only 44mg/1.1mL vials or only 76mg/1.9mL vials are not classified under any SUD exposure group but will remain part of the study population.
	

Figure 2 illustrates possible elranatamab administration scenarios for each SUD group. These examples are not exhaustive and do not represent all potential administration schedules.

090177e1a4a71ff1\Approved\Approved On: 05-Nov-2025 14:15 (GMT)

Figure 2. SUD Periods Administration Schedule

[figure not shown]

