Table 2 summarizes the patient exposure groups and assessment periods during which endpoints for each study objective will be measured. Patients will be included in the follow-up sub-period analyses if they have at least one claim for elranatamab or if the end date of their follow-up period falls within the sub-period's time frame.

Table 2. Patient Exposure Groups Stratification and Assessment Period for Study Objectives

Study Objective	Assessment period	Patient Exposure Groups
Objective 1 – Patient Characteristics	Baseline period	Study population
	Index date	Group A, Group A+B, Group C
Objective 2 – Treatment administration, dosing and timing	SUD period 
 Overall (Between first 44mg/1.1mL vial – first 76mg/1.9mL vial) Between first 44mg/1.1mL vial – second 44mg/1.1mL vial Between second 44mg/1.1mL vial – first 76mg/1.9mL vial 	Group A, Group A+B, Group C
	Follow-up period 
 Index date 	Study population

090177e1a4a71ff1\Approved\Approved On: 05-Nov-2025 14:15 (GMT)

Study Objective	Assessment period	Patient Exposure Groups
	
 • Index date (day 1) to day 8 • Day 9 to day 168 • Day 169 to end of follow-up period • Overall (day 1 to end of follow-up period) 	
Objective 3 – HCRU and costs	HCRU baseline assessment period	Study population
	SUD period 
 • Overall (Between first 44mg/1.1mL vial – first 76mg/1.9mL vial) • Between first 44mg/1.1mL vial – second 44mg/1.1mL vial • Between second 44mg/1.1mL vial – first 76mg/1.9mL vial 	Group A, Group A+B, Group C
	Follow-up period 
 • Index date • Index date (day 1) to day 8 • Day 9 to day 168 • Day 169 to end of follow-up period • Overall (day 1 to end of follow-up period) 	Study population
Objective 4 – Other MM treatments including supportive therapy	Follow-up period 
 • Index date • Index date (day 1) to day 8 • Day 9 to day 168 • Day 169 to end of follow-up period • Overall (day 1 to end of follow-up period) 	Study population
Objective 5 – Known adverse events	CRS/ICANS follow-up assessment period (CRS/ICANS events)	Group A, Group A+B, Group C
	SUD period (Cytopenia events) 
 • Overall (Between first 44mg/1.1mL vial – first 76mg/1.9mL vial) 	Group A, Group A+B, Group C

090177e1a4a71ff1Approved\Approved On: 05-Nov-2025 14:15 (GMT)

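### Objective 5 is tabulated only by step-up groups formed after index, which the adverse events may themselves shape and which leave out patients who stop during step-up, so group differences cannot be read as related to step-up timing

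*Protocol*

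**What the plan says.** The abstract (Exposure of interest) sets the principle: "Analyses of outcomes during the SUD period will also be stratified based on types of elranatamab exposure during that time".

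Section 9.3.1, Table 1 gives the SUD group the role of exposure and defines it from events after index:

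- Group A: "second 44mg/1.1mL vial is received 1 to 7 days after the first", with the same limit for the step to the first 76mg vial.
- Group B: two 44mg vials and then a 76mg vial, "with one or both intervals between doses ranging from 8 to 14 days".
- Group C pools three patterns: "patients in the study population with only one 44mg/1.1mL vial prior to receiving a 76mg/1.9mL vial"; more than two such vials; and "more than 14 days between the first and second 44mg/1.1mL vial or between the second 44mg/1.1mL vial and the first 76mg/1.9mL vial".
- No group: "patients who received only 44mg/1.1mL vials or only 76mg/1.9mL vials are not classified under any SUD exposure group". They stay in the study population.

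Table 2 reports Objective 5 for Group A, Group A+B and Group C, with no row for the study population. Cytopenia is assessed over the SUD period and its two sub-intervals. CRS and ICANS have their own window in Section 9.2: "CRS/ICANS follow-up assessment period: defined as the 14-day window post index date".

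Section 9.7 says endpoints are reported by the Table 2 groups. Section 9.7.6 plans no sensitivity analysis. Section 9.9 does not mention that group membership is determined after index. Section 9.1 states that all analysis is descriptive, without statistical comparison between exposure groups.

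**The concern.** A patient's group is known only once the first 76mg vial has been given, yet the outcomes are counted from index or from the first 44mg vial. Grouping and outcome share the same days. If an event after one vial leads to a late or additional vial, the event has helped to place the patient in Group B or C. The group is then partly a result of the outcome listed under it.

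A second selection works alongside the first. A patient who stops during step-up has no 76mg vial, belongs to no group and is absent from every Objective 5 stratum. If stopping is related to toxicity, all the columns are affected, and no overall row shows what was lost.

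At stake is the reading of the safety tables of a study designated as a PASS and planned for publication. Side-by-side columns for timely and alternative step-up invite a reading about schedule that the data cannot support.

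**Working it through.** The protocol gives no event rates and no probability that an event delays a dose, so there is no figure of the plan to reproduce. The dates follow from the protocol; every rate below is an assumption.

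**1. Overlap of windows.** Adding the two Table 1 intervals gives the day of the first 76mg vial after index:

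- Group A: 1+1 to 7+7 = 2 to 14 days.
- Group B: 8+1 to 14+14 = 9 to 28 days.
- Group C, extremely untimely: at least 15+1 = 16 days.

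The 14-day CRS/ICANS window thus overlaps the group-defining intervals. It reaches the first 76mg vial of every Group A patient but of no extremely untimely patient.

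**2. The mechanism alone.** Let p be the CRS risk after the first vial, the same for everyone, and d1 and d0 the probability of a delayed next vial with and without CRS.

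- CRS among timely = p(1−d1) / [p(1−d1) + (1−p)(1−d0)]
- CRS among delayed = p·d1 / [p·d1 + (1−p)·d0]

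With p = 0.5, d1 = 0.3, d0 = 0.1: 0.35/0.80 = 43.8% and 0.15/0.20 = 75.0%, a gap of 31 points with no timing effect. Over p = 0.3, 0.5, 0.7 and d1 = 0.2, 0.3, 0.4, with d0 = 0.1, the gap runs from 14.9 to 40.9 points.

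Table 2 has no column for delayed patients alone. If all delayed patients fall in Group B, A+B is everyone, and the display is 43.8% in A against 50% in A+B, about 6 points.

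**3. With the 14-day window added.** A simulation (1,000,000 patients per scenario) gave each dose a CRS risk independent of timing, with onset 1–2 days after the dose. Timely intervals were 2–5 days and late ones 8–14 days, except that 15% of late ones were 15–28 days. Column C holds the extremely untimely patients only.

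| CRS risk after doses 1/2/3 | Delay without / with CRS | A | B | C |
|---|---|---|---|---|
| 40/20/8% | 10% / 60% | 36.2% | 79.0% | 77.9% |
| 40/20/8% | 20% / 50% | 43.8% | 64.6% | 62.1% |
| 40/20/8% | 20% / 30% | 52.3% | 57.4% | 52.4% |
| 40/20/8% | 20% / 20% | 55.9% | 51.6% | 45.7% |
| 30/30/30% | 20% / 25% | 64.5% | 55.3% | 44.1% |

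Hand check of Group A in the second row: CRS given a timely next vial is 0.20/(0.20+0.48) = 0.294 after dose 1 and 0.10/(0.10+0.64) = 0.135 after dose 2. Then 1 − 0.706 × 0.865 × 0.92 = 0.438. As Table 2 would show it, that row reads A 43.8%, A+B 53.2%, C 62.1%.

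The C minus A difference runs from 77.9 − 36.2 = +41.7 to 44.1 − 64.5 = −20.4 points. The sign changes because delayed patients' later doses fall outside the 14 days.

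**4. Patients in no group.** If, in the second row, 30% of patients with CRS after dose 1 or 2 stop on 44mg vials only, A+B shows 45.0% while all patients have 54.0%.

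**5. Cytopenia.** The SUD period lengthens with the delay. At a constant 3% per day with no effect of events on timing, cytopenia is 21.2%, 38.2% and 55.9% in A, B and extremely untimely C, because the mean SUD period is 7.0, 15.2 and 26.6 days. This is a separate mechanism, but it also prevents a reading by group.

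**The case against.** The strongest reply is that the study is descriptive. Section 9.1 rules out measures of effect and comparisons between groups, and Objective 5 asks for incidence and prevalence, not for an effect of timing. The exposure label in Table 1 is also given to the whole study population, so it carries little causal weight. This limits the severity, but it neither makes the columns interpretable nor restores the patients who are in none of them.

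Next, nothing in the protocol says that CRS, ICANS or cytopenia delays a dose. That stands: the mechanism is plausible but assumed. Group A is also tolerant. Each interval may reach 7 days, whereas Table 10 expects three administrations by day 8, so a short delay can leave a patient in Group A.

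Part of the remedy already exists. Table 2 splits cytopenia by the two SUD intervals, Table 4 reports inter-vial times, and Table 7 reports days to first event. What is missing is an all-patient denominator and a dose-anchored count for CRS and ICANS.

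A reader might infer that the delayed groups will necessarily show more toxicity, or that a spurious gap of about 31 points is to be expected. The documents support neither. The fixed 14-day window pulls CRS and ICANS the other way, Table 2 never shows delayed patients alone, and Group C also holds patients classified by vial count.

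**Conclusion.** The point holds as a limit on interpretation. Objective 5 is tabulated only in strata that form after index, share time with the outcomes and may be altered by them. Patients who stop during step-up are in none of these strata. These facts come from Tables 1 and 2 and Section 9.2 and need no assumption.

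The size and direction of the distortion are not known. Events that delay doses move toxicity into B and C; the fixed 14-day window leaves later doses of delayed patients unobserved. In the five scenarios the CRS difference between extremely untimely patients and Group A ran from +41.7 to −20.4 points with no timing effect. That range rests wholly on assumed event and delay probabilities. It shows that the contrast is uninformative and does not predict the result. Because the study is descriptive, this is a change the plan should make, not a defect that invalidates the study.

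**What to change.** 1. In Table 2, add the whole study population, including patients in no SUD group, as the main Objective 5 result.
2. Report new CRS, ICANS and cytopenia after the first 44mg, second 44mg and first 76mg vial, each up to the next dose or a fixed number of days, with all recipients of that vial as denominator. For cytopenia, a fixed number of days also removes the dependence on SUD length.
3. Report the interval to the next vial by whether an event preceded it.
4. If the A, A+B and C tables are kept, split events into those before and those after the interval that set the group.
5. State in Section 9.9 that group membership is determined after index and may be a consequence of the events.

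The cost is wording in Tables 2 and 7 and Section 9.9 plus some table rows. Tables 4 and 7 already need the dose and event dates. The downside is small counts per dose interval, given 128 patients with an elranatamab claim at the February 2025 cut.
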